14.3. PHARMACODYNAMIC ANALYSIS

14.3.1 PHARMACODYNAMIC VARIABLES AND DERIVATION

At each visit during the Treatment Period, samples will be collected for measurement of the following cytokines and chemokines: IL-6, CCL2, CXCL8 (IL-8), CXCL4 (MCP-1), TGF β , CTGF, ICAM-1, VEGF, IL-4, IL-10, and IL-1 β .

14.3.2 MISSING DATA METHODS FOR PHARMACODYNAMIC VARIABLE

Missing data will not be imputed, unless otherwise stated.

14.2.3 ANALYSIS OF PHARMACODYNAMIC VARIABLE

The observed values and change from baseline values will be listed for each participant at each protocol specified visit and will be summarised using descriptive statistics over time by treatment

Document: \$506df00529e1\$BDE32479744D47F0B3BAA4285D5BE091.docx

Author: ████████████████████

Version Number:

Final v1.1

Version Date:

16Nov2022

Template No.: CS_TP_BS016 Revision 6

Reference: CS_WI_BS005

Effective Date: 02Dec2019

Copyright © 2009, 2010, 2012, 2016, 2018, 2019 IQVIA. All rights reserved. The contents of this document are confidential and proprietary to IQVIA Holdings Inc. and its subsidiaries. Unauthorized use, disclosure or reproduction is strictly prohibited.

group and for all participants.

15. SAFETY OUTCOMES

All safety summaries will be based on the Safety Analysis Set.

There will be no statistical comparisons between the treatment groups for safety outcomes.

15.1. ADVERSE EVENTS

AEs will be coded to system organ class (SOC) and preferred term (PT) using MedDRA central coding dictionary, Version 23.0 (or higher).

Treatment-emergent adverse events (TEAEs) are defined as AEs which commence or worsen on or after the date and time of first study drug administration. AEs without an onset date and time will be defined as treatment-emergent except if an incomplete date (e.g., month and year) clearly indicates that the event started prior to start of first study drug administration or if the AE stop date indicates that the event started and/or stopped prior to start of first study drug administration.

All Adverse Events (AEs) summaries will be restricted to the TEAEs only. The number and percentage of TEAEs, Serious TEAEs, TEAEs leading to discontinuation of study treatment and study, and TEAEs related to study treatment will be summarized by SOC, PT and treatment group. The number and percentage of TEAEs by maximum severity will also be summarized.

An overall summary of the number and percentage of participants who had events in each of the categories described below will be produced by treatment group and for all participants.

The following AE summaries will be provided:

- Overview of TEAEs, including:
 - o At least one TEAE
 - o At least one study treatment related TEAE
 - o At least one serious TEAE
 - o At least one study treatment related serious TEAE
 - o Any TEAE leading to death
 - o TEAE leading to study discontinuation
 - o TEAE leading to study drug withdrawal
 - o TEAE leading to study drug interruption
 - o At least one TEAE by maximum severity
 - o At least one study treatment related TEAE by maximum severity
- Incidence of TEAEs by SOC and PT
- Incidence of study treatment related TEAEs by SOC and PT

Document: \$506df00529e1\$BDE32479744D47F0B3BAA4285D5BE091.docx

Author: ████████████████████

Version Number:

Final v1.1

Version Date:

16Nov2022

Template No.: CS_TP_BS016 Revision 6

Reference: CS_WI_BS005

Effective Date: 02Dec2019

Copyright © 2009, 2010, 2012, 2016, 2018, 2019 IQVIA. All rights reserved. The contents of this document are confidential and proprietary to IQVIA Holdings Inc. and its subsidiaries. Unauthorized use, disclosure or reproduction is strictly prohibited.

- Incidence of TEAEs by maximum severity
- Incidence of study treatment related TEAEs by maximum severity
- Incidence of serious TEAEs by SOC and PT
- Incidence of study treatment related serious TEAEs by SOC and PT.

In the summary tables, AEs will be presented by decreasing frequency of total participants overall within each SOC and then similarly by decreasing frequency of total participants overall within each PT. SOC or PTs with equal frequencies will be sorted alphabetically.

An overall summary of number of participants within each of the categories described in the subsection below, will be provided as specified in the templates.

The overall Listing of adverse events will include TEAEs and Non-TEAEs. All other listings will include TEAEs only.

15.1.1 ALL TEAEs

Incidence of TEAEs will be presented by SOC and PT and broken down further by maximum severity and relationship to study treatment. In these tables, SOC and PT will be presented by decreasing frequency.

15.1.1.1 SEVERITY

Adverse event severity is classified as mild, moderate, or severe. TEAEs starting after the first dose of study treatment with a missing severity will be classified as severe. If a participant, reports a TEAE more than once within that SOC/ PT, the AE with the worst-case severity will be used in the corresponding severity summaries.

15.1.1.2 RELATIONSHIP TO STUDY TREATMENT

Relationship to study treatment, as assessed by the Investigator, is classified as definitely related, probably related, possibly related, unlikely related or not related. TEAEs reported as having a definitely related, probably related, or possibly related relationship to study treatment are classified as related. TEAEs with a missing or unknown relationship to study treatment will be considered related to study treatment. If a participant, reports the same AE more than once within that SOC/ PT, the AE with the worst relationship to study treatment will be used in the corresponding relationship summaries.

15.1.1.3 TEAEs LEADING TO STUDY DRUG INTERRUPTION

TEAEs leading to drug interruption will be identified by using the variable pertaining to action taken with study treatment on the AE page of the eCRF indicated as 'Drug interrupted' and all TEAEs meeting this criteria will be listed separately.

Document: \$506df00529e1\$BDE32479744D47F0B3BAA4285D5BE091.docx

Author: [REDACTED]

Version Number: Final v1.1

Version Date: 16Nov2022

Template No.: CS_TP_BS016 Revision 6

Reference: CS_WI_BS005

Effective Date: 02Dec2019

Copyright © 2009, 2010, 2012, 2016, 2018, 2019 IQVIA. All rights reserved. The contents of this document are confidential and proprietary to IQVIA Holdings Inc. and its subsidiaries. Unauthorized use, disclosure or reproduction is strictly prohibited.

15.1.1.4 TEAEs LEADING TO STUDY DRUG WITHDRAWAL

TEAEs leading to permanent discontinuation of study drug will be identified by using the variable pertaining to action taken with IP on the AE page of the eCRF indicated as 'Drug withdrawn' and all TEAEs meeting this criteria will be listed separately.

15.1.1.5 TEAEs LEADING TO STUDY DISCONTINUATION

TEAEs leading to study discontinuation will be identified by using the variable pertaining to 'specify action taken' on the AE page of the eCRF indicated as 'Withdrawn from study' and all TEAEs meeting this criteria will be listed separately.

15.1.1.6 ADVERSE EVENTS LEADING TO DEATH

TEAEs leading to death will be identified by using the variable pertaining to seriousness criteria on the AE page of the eCRF indicated as 'Death' and all TEAEs leading to death will be listed separately.

15.1.1.7 SERIOUS ADVERSE EVENTS

Serious adverse events (SAEs) are those events recorded as "Serious" on the AE page of the eCRF and all Serious Treatment-Emergent AEs will be summarized and listed separately.

15.2. LABORATORY EVALUATIONS

Central safety laboratory results will be included in the reporting of this study for haematology, biochemistry, coagulation, urinalysis, and serum pregnancy testing. No lab data imputation will be performed. Incomplete data may be excluded from some analyses. In cases where an analysis depends on identifying an abnormal value, only values which are non-missing and which can be clearly identified programmatically as abnormal will be counted.

Presentations will use SI Units, as provided by the laboratory.

Quantitative laboratory measurements reported as "<X", i.e. below the lower limit of quantification, or "> X", i.e. above the upper limit of quantification, will be converted to X for the purpose of quantitative summaries, but will be presented as recorded, i.e. as "<X" or "> X" in the listings.

Laboratory data will be summarized using descriptive statistics. Clinical laboratory data collected during study conduct, which were not required per protocol, such as for special testing to evaluate an AE, will be listed and not summarized.

All laboratory data is summarised and listed for all visits where data is collected. The following summaries are provided for laboratory data:

Actual values and change from baseline will be summarized using descriptive statistics at each protocol specified time point, by treatment group.

- Shift from baseline will be summarized at each post-baseline protocol scheduled time by treatment group, using frequency tabulations.

Document: \$506df00529e1\$BDE32479744D47F0B3BAA4285D5BE091.docx

Author: [REDACTED]

Version Number: Final v1.1

Version Date: 16Nov2022

Template No.: CS_TP_BS016 Revision 6

Reference: CS_WI_BS005

Effective Date: 02Dec2019

- Separate listings will be produced for all participants with at least one out-of-range or abnormal clinical laboratory result. In these listings, the full time point profile will be presented for the parameter with the out-of-range or abnormal value.

A list of laboratory assessments to be included in the outputs is included below:

- Haematology: Haemoglobin, haematocrit, red blood cell count, red cell distribution width, mean corpuscular volume, mean corpuscular haemoglobin, mean corpuscular haemoglobin concentration, white blood cell count, neutrophils, lymphocytes, monocytes, eosinophils, basophils, and platelet count
- Biochemistry: Sodium, potassium, magnesium, bicarbonate, phosphate, calcium, urea, urate, serum albumin, total protein, gamma-glutamyl transferase, alanine transaminase, aspartate transaminase, direct bilirubin, alkaline phosphatase, glucose, cholesterol, triglycerides, high-density lipoprotein, low-density lipoprotein, creatine phosphokinase, lactate dehydrogenase, creatinine, eGFR.
- Coagulation: Activated partial thromboplastin time (aPTT), Prothrombin time, International normalized ratio (INR), Fibrinogen
- Urinalysis: urine culture, sensitivities, antibiotic susceptibility, urine albumin, urine creatinine, urinary albumin creatinine ratio (UACR)

LABORATORY SPECIFIC DERIVATIONS

Unit conversions for laboratory data will be provided in the programming specifications documents.

LABORATORY REFERENCE RANGE

Continuous laboratory measurements will be compared with the relevant laboratory reference ranges by the laboratory vendors and categorized as:

- Low: Below the lower limit of the laboratory reference range.
- Normal: Within the laboratory reference range (upper and lower limit included).
- High: Above the upper limit of the laboratory reference range.
- Laboratory values that do not have a reference range will not be categorized.

15.3. 12-LEAD ELECTROCARDIOGRAM EVALUATIONS

12-Lead Electrocardiogram (ECG) parameters (heart rate [beats/min], PR interval[msec], QRS duration[msec], QT interval [msec], QTcf interval [msec], QTcB interval [msec] and RR interval [msec]) will be reported for this study.

The following summaries will be provided for ECG data:

- All ECG data will be presented in data listings.

Document: \$506df00529e1\$BDE32479744D47F0B3BAA4285D5BE091.docx

Author: [REDACTED]

Version Number:

Final v1.1

Version Date:

16Nov2022

Template No.: CS_TP_BS016 Revision 6

Reference: CS_WI_BS005

Effective Date: 02Dec2019

- Actual values and change from baseline for ECG parameter values will be summarized using descriptive statistic at each protocol specified time point by treatment group .
- Shift from baseline according to the investigator's interpretation of ECG results (Normal, Abnormal NCS, Abnormal CS) will be summarized at each post-baseline protocol scheduled time by treatment group , using frequency tabulations.

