#### **5.4.8 Stopping Rules / Discontinuation Criteria**

##### **5.4.8.1 Individual Participant Stopping Rules**

Safety laboratory testing will be performed by a study central laboratory.

If ALT or AST > 3 x ULN, the participant must have repeat testing conducted within 48 to 72 hours to confirm the values.

If the elevation is confirmed as >3 x ULN, close observation that includes elicitation of a detailed history and performance of diagnostic laboratory studies to exclude other causes of acute liver injury must be conducted. In addition, participants must have their liver chemistry (ALT, AST, ALP, international normalised ratio (INR) and total bilirubin) retested at least once weekly until levels normalise or return to baseline.

In the event of confirmed laboratory results (i.e. confirmed on retest within 48 to 72 hours) meeting any of following criteria, IMP will be stopped permanently for that participant:

- ALT or AST >8 x ULN
- ALT or AST >5 x ULN for more than 2 weeks
- ALT or AST >3 x ULN and either bilirubin >2 x ULN or INR >1.5
- ALT or AST >3 x ULN with the appearance of fatigue, nausea, vomiting, right upper quadrant pain or tenderness, fever, rash, and/or eosinophilia (>5%).

If serum creatinine is  $\geq$  Grade 3 (based on the Common Terminology Criteria for Adverse Events (CTCAE)), IMP will be stopped for that participant and they will be monitored until values return to Grade 1. IMP may then be restarted but stopped permanently if there is a recurrence of serum creatinine levels  $\geq$  Grade 3.

All participants should attend the follow up visit 4 weeks after their last dose of IMP.

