#### **12.4.2.3 Laboratory Results**

Laboratory data will be summarised and listed by treatment group and visit. Actual values and the changes from baseline will be presented. In addition, 'shift from baseline' tables will also be presented showing the changes in the reference range classifications (normal, low, high) over time.

Dipstick urinalysis results evaluation (normal or, abnormal not clinically significant or abnormal clinically significant) will be summarised by treatment group and visit using frequency tabulations.

Abnormal laboratory values (including clinical significance as assessed by the Investigator) will be flagged in the listings.

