APPENDIX 3. TABLES AND LISTINGS FOR DSMB MEETINGS

TABLES

- STUDY DISPOSITION, ALL PARTICIPANTS ENROLLED SET
- DEMOGRAPHICS, INTENTION-TO-TREAT SET
- DISEASE HISTORY, SAFETY ANALYSIS SET
- TREATMENT-EMERGENT ADVERSE EVENTS, SAFETY ANALYSIS SET
- TREATMENT-EMERGENT SEVERE ADVERSE EVENTS, SAFETY SET
- TREATMENT-EMERGENT SERIOUS ADVERSE EVENTS, SAFETY SET
- TREATMENT RELATED TREATMENT-EMERGENT ADVERSE EVENTS, SAFETY SET
- CLINICALLY SIGNIFICANT LABORATORY VALUES , SAFETY SET
- ELECTROCARDIOGRAM FINDINGS, SAFETY SET
- SCLERODERMA RELATED CONCOMITANT MEDICATIONS , SAFETY SET

LISTINGS

- STUDY DISPOSITION, INTENTION-TO-TREAT SET
- DEMOGRAPHICS, INTENTION-TO-TREAT SET
- DISEASE HISTORY, INTENTION-TO-TREAT SET
- CONCOMITANT MEDICATION, SAFETY ANALYSIS SET
- PARTICIPANT QUESTIONNAIRES, PHYSICAL EXAMINATIONS, VITAL SIGNS MEASUREMENTS
- ADVERSE EVENTS, SAFETY SET
- SERIOUS ADVERSE EVENTS, SAFETY SET
- ADVERSE EVENTS LEADING TO DISCONTINUATION OF STUDY DRUG, SAFETY SET
- LABORATORY MEASURES, SAFETY SET
- ELECTROCARDIOGRAM, SAFETY SET

Document: \$506df00529e1\$BDE32479744D47F0B3BAA4285D5BE091.docx

Author: ████████████████████

Version Number: Final v1.1

Version Date: 16Nov2022

Template No.: CS_TP_BS016 Revision 6

Reference: CS_WI_BS005

Effective Date: 02Dec2019

Copyright © 2009, 2010, 2012, 2016, 2018, 2019 IQVIA. All rights reserved. The contents of this document are confidential and proprietary to IQVIA Holdings Inc. and its subsidiaries. Unauthorized use, disclosure or reproduction is strictly prohibited.

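### The laboratory tables called for in the SAP text put every ALT or AST value above ULN in one High class and count no participants at the protocol's own liver or creatinine thresholds

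*SAP*

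**What the plan says.** SAP 15.2 names two laboratory tables. The first is "Actual values and change from baseline will be summarized using descriptive statistics at each protocol specified time point, by treatment group". The second is "Shift from baseline will be summarized at each post-baseline protocol scheduled time by treatment group, using frequency tabulations". The same section defines the classes as Low, Normal and "High: Above the upper limit of the laboratory reference range". Protocol 12.4.2.3 plans the same three classes: its shift "tables will also be presented showing the changes in the reference range classifications (normal, low, high) over time". Beyond that, SAP 15.2 provides listings: "Separate listings will be produced for all participants with at least one out-of-range or abnormal clinical laboratory result", with the full time profile of the affected parameter.

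Protocol 5.4.8.1 uses a different scale. An ALT or AST above 3 x ULN leads to a repeat test in 48 to 72 hours and, if confirmed, to liver chemistry at least weekly. Four confirmed liver criteria end treatment for the participant: above 8 x ULN; above 5 x ULN for more than 2 weeks; "ALT or AST >3 x ULN and either bilirubin >2 x ULN or INR >1.5"; and above 3 x ULN with listed symptoms or eosinophilia. A further rule covers creatinine at CTCAE Grade 3 or higher. Protocol 5.4.8.2 then counts participants: three on the same rule, or five on any, halt recruitment pending DSMB review.

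SAP 6.7 leaves unscheduled measurements out of the by-visit summaries. SAP 15.2 adds that tests outside the protocol schedule, such as those done to evaluate an AE, are listed only. For the DSMB, SAP Appendix 3 names a table titled "CLINICALLY SIGNIFICANT LABORATORY VALUES , SAFETY SET", with no threshold stated, and a listing of laboratory measures.

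**The concern.** Safety and tolerability against placebo is the first of the two secondary objectives, and the individual stopping rules show that the protocol watches liver and renal toxicity most closely. The planned tables do not report on the scale of those rules. Exclusion criterion 11 bars ALT, AST or bilirubin above ULN at Screening or Baseline. In an eligible participant, every later ALT or AST value above ULN is therefore the same Normal-to-High shift, however large it is. The tables also take one analyte at a time, so a criterion that joins ALT/AST with bilirubin or INR cannot be read from them, and the SAP does not grade creatinine.

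At stake is whether the report can state, per arm, how many participants passed 3, 5 or 8 x ULN, met a combined liver criterion, or reached creatinine Grade 3. Followed as written, the SAP text leaves that count to be made by hand from listings.

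**Working it through.** The plan gives no figure to reproduce here, and there is no formal sample size calculation. The inputs are the class definitions (SAP 15.2), the cut-offs (protocol 5.4.8.1), the summary statistics (SAP 6.1: mean, SD, median, minimum, maximum) and 10 participants per arm (SAP 3.1).

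**Step 1. Apply the SAP classes to values in multiples of ULN.**

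| ALT or AST (x ULN) | SAP class | Cut-offs crossed, of 3, 5 and 8 |
|---|---|---|
| 1.1 | High | 0 |
| 3.1 | High | 1 |
| 5.1 | High | 2 |
| 8.1 | High | 3 |
| 10 | High | 3 |

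**Step 2. Compare arms of 10 at one visit.** Assumption: unaffected participants are at 0.6 x ULN. With one raised value x, mean = (9 × 0.6 + x)/10. SD = square root of (sum of squared deviations / 9).

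| Raised values | Shift to High | Median | Mean | SD | Maximum | Count >3x | Count >8x |
|---|---|---|---|---|---|---|---|
| one at 1.1 | 1/10 | 0.6 | 6.5/10 = 0.65 | √(0.225/9) = 0.16 | 1.1 | 0/10 | 0/10 |
| one at 10 | 1/10 | 0.6 | 15.4/10 = 1.54 | √(79.524/9) = 2.97 | 10 | 1/10 | 1/10 |
| two at 10 | 2/10 | 0.6 | 24.8/10 = 2.48 | √(141.376/9) = 3.96 | 10 | 2/10 | 2/10 |

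The shift cell and the median do not separate the first two rows. The mean, SD and maximum do, so an extreme scheduled value would leave a trace. None of them is a count of participants above a cut-off. Only the last two columns are, and the SAP text does not call for them.

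**Step 3. Look across visits and analytes.** One participant in High at each of Weeks 4, 8 and 12 could be one person three times or three people once, because the tables are per visit. Duration above 5 x ULN, and bilirubin or INR in the same participant, cannot be recovered from them.

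**Step 4. Compare the timing.** Scheduled post-baseline laboratory visits are Weeks 4, 8, 12 and 16. Confirmatory tests at 48 to 72 hours and weekly follow-up tests fall between them. Under SAP 6.7 such values stay out of the by-visit summaries, so a peak between visits may appear in no table. The sentence on retests in SAP 6.7 also leaves unclear whether the repeat or the initial result is used.

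**Step 5. Ask whether the table could be empty.** The documents give no event rate. For assumed true rates p, the chance of at least one case among 20 FT011 participants is 1 − (1 − p)^20: 64% at p = 5%, 88% at 10% and 99% at 20%.

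**The case against.** The strongest reply is that the information survives and the study is small. Each out-of-range result brings a full-profile listing, ordered by treatment group, and about 30 profiles can be read by hand. The per-visit maximum, mean and SD respond to an extreme value. Meeting a liver rule ends treatment, and SAP 9.1 counts drug discontinuations per arm with the primary reason, while SAP 15.1 counts TEAEs leading to drug withdrawal or interruption. The SAP agrees with the protocol, so there is no contradiction between the two on laboratory tables. All of this stands. It limits the point to tabulation, but none of these outputs counts threshold crossings. Protocol 10.1 and 10.3 leave reporting a laboratory change as an AE largely to the investigator's judgement.

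A reader might go further than the documents allow in four ways.

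- That the DSMB could not apply the study stopping rules. Protocol 5.4.8.2 triggers an immediate review when its conditions are met, and nothing there makes this depend on a periodic SAP table.
- That the DSMB laboratory table shows only values that the investigator calls significant. Appendix 3 gives a title alone; investigator assessment comes from protocol 12.4.2.3, which describes flags in listings.
- That no threshold table exists anywhere. SAP 8 and 4.1 refer to separate templates and a DSMB charter that are not among the documents.
- That any rise reads as Normal-to-High. A rise within the reference range stays Normal, and exclusion 11 does not cover creatinine, so the baseline argument applies to the liver tests only.

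A further sentence in SAP 15.2 says that laboratory data are summarised for all visits with data. The two tables it then defines are tied to protocol time points, so it does not bring unscheduled values in.

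**Conclusion.** The point holds as a gap in tabulation. The SAP text calls for no table that counts participants per arm at the protocol 5.4.8.1 liver or creatinine thresholds. Its single High class merges values crossing none and all of the 3, 5 and 8 x ULN cut-offs, and SAP 6.7 leaves between-visit retests out of the by-visit summaries. In the illustrative arm of 10, the shift table shows 1/10 where the count above 8 x ULN could be 0/10 or 1/10.

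This is a cheap improvement to a secondary safety objective and should be made. It is not a defect of validity: the primary objective is PK, SAP 15 plans no statistical comparison of safety between arms, and the data remain in listings. The illustration rests on the assumed 0.6 x ULN for unaffected participants, and the 64% to 99% range on assumed event rates. The conclusion about classes and counts needs neither.

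**What to change.** Add to SAP 15.2 one table by treatment group and pooled FT011, with each participant counted once. It should give:

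- the worst post-baseline ALT or AST in bands at the protocol's own cut-offs (<=1x, >1-3x, >3-5x, >5-8x, >8x ULN);
- the worst creatinine grade under CTCAE v5.0, which the protocol cites without a numeric cut-off;
- the number recorded as meeting each individual stopping rule in protocol 5.4.8.1, with confirmation on retest applied as the protocol defines it and the symptom criterion taken from AE data.

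The ALT/AST bands and the creatinine grade should use scheduled and unscheduled central-laboratory values, under a stated exception to SAP 6.7. The same edit should make clear how a retest and the result it repeats are handled. If DSMB meetings remain (the SAP is dated November 2022, after the planned completion in the third quarter of 2022), add the table to Appendix 3 in masked form.

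One matter must be settled before the joint liver criterion is tabulated. The laboratory panels in protocol 8.2 and SAP 15.2 list only direct bilirubin. Protocol 5.4.8.1 names total bilirubin for monitoring and just bilirubin in the stopping rule. These passages must be reconciled; this review takes no position on which is right.

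The bands, the creatinine grade and the stopping-rule counts only report against rules that the protocol already sets. They need no new visits, and the downside is a little more programming. Whether the joint criterion can be tabulated from values already collected depends on how the bilirubin passages are reconciled.
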